A variable that may alter the survival of US-guided IVs that has not been studied extensively is the length of catheter that resides in the vein. Currently the general accepted rule is that an "adequate" amount of the catheter should be in the vein to avoid failure of the catheter.¹¹⁻¹⁴ However, this recommendation is only anecdotal and there has been no study to verify or quantify it. Our preliminary data focused on defining this relationship. In our study, **100% of catheters failed** in which less than 30% of the catheter was placed within the vein and **no failures** in those IVs in which at least 65% of the catheter was in the vein. All catheters in this analysis were commonly available 4.78 cm IVs. A key challenge for inserters is that achieving this quantity of catheter length in vein is impractical at the recommended angle of insertion when considering deeper target vessels. For many institutions, including ours, the 4.78 option is the longest stocked IV catheter and catheter survival is negatively impacted.

Central Hypothesis/Objectives:

We hypothesize that using an Ultra Long IV (6.35 cm) catheter increases the likelihood of ensuring a higher quantity of the catheter in the vessel lumen and leads to improved catheter longevity.

Primary Objective: Compare the IV survival between the Ultra Long IV (UL IV) (6.35 cm/20G) and the Standard Long IV (SL IV) (4.78 cm/20G) placed under US-guidance.

Function is defined as ability of catheter to flush 5 mL without resistance with or without blood sampling.

Secondary/Tertiary Objective(s):

Determine catheter survival based on vein depth.

Determine optimal cutoff length of catheter in vein for best survival profile.

Determine catheter survival based on angle of insertion.

Quantify specific etiologies related to premature catheter failure comparing UL IV to the SL IV.

Quantify overall costs associated with placement of the UL IV compared to the SL IV.

Determine overall success of placement UL IV versus SL IV.

Determine first-stick success UL IV compared to SLIV.

Determine number of attempts and time to insertion comparing UL IV to SL IV.

Safety Endpoint(s):

Compare phlebitis and thrombosis complication rates between the Ultra Long IV and the Standard Long IV.

[figure not shown]
Compare infection rates for all catheters.

Study Design:

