Appendix E represents the data collection documentation tool for all medications.

SVT and DVT rates will be calculated based on upper extremity proven diagnosis of SVT and/or DVT in symptomatic cases. Researchers will review all study subject records in EPIC and screen for all upper extremity venous Doppler examinations. Radiology interpretations will be reviewed for findings of consistent with thrombus. This review will occur thirty days post patient discharge.

Infection rate will be tracked using confirmed blood stream infection data from epidemiology. These are cases in which line sepsis or bacteremia is confirmed by positive blood cultures.

Cost difference between approaches will be tracked. Equipment costs and personnel costs will be tracked. Number and type of IV catheters inserted/attempted will be extracted from the medical record. Supply costs will be estimated based on number of IVs attempted. Median time to successful catheter placement will serve as a baseline for estimating time needed for future reinsertions. Time will be assigned a monetary value. We will also track the number of patients from each group that require a PICC or CVC as a rescue catheter.

Sample Size and Power Analysis:

For this randomly allocated two-groups experiment, the primary outcome is catheter survival. Sample size calculation is based on primary outcome: composite or all cause premature removal due to complication of the IV catheter. Based on literatures and a new published article immediately prior to study period, we estimate sample size using the median survival time 30 hours for the 4.78 cm standard IV option. 91 subjects per group for a total sample size of 182 subjects is the minimum recommendation assuming a 10% dropout rate. This calculation

achieves power of 80% to detect a hazard ratio of 0.63 or less for line failure of the 6.35 cm ultra long IV based on log-rank test.

Statistical Analysis:

Characteristics of enrolled and eligible patients will be summarized between two arms using means [standard deviations] and medians [interquartile ranges] compared by t-tests or Wilcoxon tests for continuous variables and frequencies (percentages) compared by chi-squared tests or Fisher's exact tests for categorical variables.

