Survival analysis methods (Kaplan-Meier curves, the log-rank test for continuous failure times or logistic model for discrete failure times) will be used for analyzing times to IV failure with non-failure times treated as censored. Proportions of SVT, DVT and catheter infection rates will be reported separately for each arm. Nonparametric summaries and a Wilcoxon Rank sum test will be used for the cost data. To test the effect of catheter variables on survival, we will further use Cox proportional hazard regression models for time-to-event outcomes and logistic regression models for binary outcomes. P-values of less than 0.05 will be considered statistically significant. Analysis will be conducted using SAS 9.4.

Study Site:

William Beaumont Hospital, Royal Oak (RO) campus is the proposed site for the investigation. It is a 1,100 bed major academic and referral center with Level 1 adult trauma and Level 2 pediatric trauma status. A major teaching facility, Beaumont, Royal Oak has 55 residency and fellowship programs with 454 residents and fellows. Beaumont is the exclusive clinical partner for the Oakland University William Beaumont School of Medicine. The Beaumont Research Institute was established more than 30 year ago at Royal Oak and offers research support services to clinical investigators.

The Royal Oak (RO) Emergency Center (EC) has the resources available to complete this project. This site is a tertiary care, level I trauma center with an annual ED census greater than 130,000 visits. I collaborated with nursing leadership in 2015 and implemented an ancillary staff-training program for placing US-guided IVs. Nearly forty ancillary staff members are certified in this procedure. Further, weekly logs of IVs placed under US-guidance show that an average of 10 US-guided IVs are placed daily. The RO EC has 130,000 annual visits of which many patients have difficult access. We also have 11 portable US machines with high frequency linear transducers that are ideal for vascular imaging.

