Beaumont Health is Michigan's largest health care system and is the most preferred for health care in the tri-county area, according to National Research Corporation survey data. A not-for-profit organization, it was formed in 2014 by Beaumont Health System, Botsford Hospital and Oakwood Healthcare to provide patients with the benefit of greater access to extraordinary, compassionate care, no matter where they live in Southeast Michigan. Beaumont Health has total net revenue of \$4.5 billion and consists of eight hospitals with 3,429 beds, 187 outpatient sites,

nearly 5,000 physicians, 38,000 employees and 3,500 volunteers. In 2017, Beaumont Health had 175,700 inpatient discharges, 17,800 births and 575,000 emergency visits.

Potential Impact:

Optimization of peripheral vascular care is a critical strategy to improve patient outcomes and reduce health care costs. Enhanced dwell times will lead to improved patient/staff satisfaction, decreased interruptions in care with shorter hospital length of stay, and decrease in complications such as thrombosis, bleeding, and infection. Over 2 billion IV catheters are used worldwide annually with less than one-third of catheters actually ending up in a patient. No other industry would accept this degree of failure in its most essential and necessary process to deliver care. In a study by Rickard et al in 2012, a patient required an average of 1.7 IV catheters per admission.¹⁵ With a cost of approximately \$35 per catheter for straightforward insertions, even a slight improvement in dwell time has the potential to save our health system millions of dollars.

References

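### The cost objective asks for overall costs, but the only stated cost analysis is a rank test with nonparametric summaries, which does not estimate a cost difference and can point the opposite way to the mean

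*Combined protocol and SAP*

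**What the plan says.** The Secondary/Tertiary Objective(s) include: "Quantify overall costs associated with placement of the UL IV compared to the SL IV". The cost paragraph at the end of the follow-up procedures states: "Cost difference between approaches will be tracked". It lists equipment and personnel costs and the number and type of catheters, and adds: "We will also track the number of patients from each group that require a PICC or CVC as a rescue catheter". For reinsertion time it says: "Median time to successful catheter placement will serve as a baseline for estimating time needed for future reinsertions", with time then given a monetary value. Potential Impact cites an average of 1.7 catheters per admission and about $35 per catheter, and argues that "even a slight improvement in dwell time has the potential to save our health system millions of dollars".

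Under Statistical Analysis, the only sentence on cost is: "Nonparametric summaries and a Wilcoxon Rank sum test will be used for the cost data". The documents name no mean cost, mean difference, confidence interval or bootstrap for cost. Means with standard deviations are planned for patient characteristics only.

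**The concern.** Overall cost and a saving to the health system are totals, and a total is the number of patients times the arithmetic mean. Medians do not add up to a total. The rank-sum test addresses a different question: how probable it is that a UL patient costs more than an SL patient.

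The two can separate in this trial because of the likely shape of the costs. Most patients would cluster at one or two catheters, and a minority would need a PICC or CVC. Any difference in unit price would touch every patient and drive the ranks. Savings from avoided rescues would sit in a few patients, and ranks register that those patients are expensive but not by how much. The trial could therefore report UL as dearer, or no different, when its mean cost is lower, or the reverse.

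**Working it through.** **Inputs from the documents.** 91 per arm, or 91 × 0.9 ≈ 82 after 10% dropout; hazard ratio 0.63 (Sample Size and Power Analysis). About $35 per catheter and a mean of 1.7 catheters (Potential Impact). Failure of 45–56% for ultrasound-guided IVs (Background). The plan gives no figure for a cost difference, so there is none to reproduce.

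**Assumed, because the documents give no value.** Rescue price R, rescue rates, any UL price premium, and the spread of other costs between patients. Tests are taken as two-sided at 0.05; the plan states 0.05 but not the sidedness.

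**1. Fixed example, 91 per arm, UL $10 dearer**

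| | SL | UL |
|---|---|---|
| No reinsertion | 60 at $35 | 69 at $45 |
| One reinsertion | 22 at $70 | 18 at $80 |
| Rescue | 9 at $35 + R | 4 at $45 + R |

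- Mean SL = (60×35 + 22×70 + 9×35 + 9R)/91 = (3,955 + 9R)/91.
- Mean UL = (69×45 + 18×80 + 4×45 + 4R)/91 = (4,725 + 4R)/91.
- UL − SL = (770 − 5R)/91, which is negative once R exceeds $154.
- R = $300: −730/91 = −$8.0. R = $500: −1,730/91 = −$19.0. R = $1,000: −4,230/91 = −$46.5.
- Medians: SL $35, UL $45, whatever the value of R.
- Pairs in which UL costs more: 69×60 + 18×82 + 4×91 = 5,980 of 91² = 8,281, so P(UL > SL) = 0.72 and Wilcoxon p = 5.5e-8.

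The rank result is the same at all three rescue prices and says that UL is dearer, while the mean says that it is cheaper.

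**2. How often: 82 per arm, rescue 15% v 5%, R = $500, premium $10 per patient**

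Cost = 35 × (1 + extra catheters) + R if rescued + premium (UL) + between-patient noise. Extra catheters are Poisson with mean 0.7 in SL, and in UL either 0.7 or 0.7 × 0.63 = 0.44. The true mean favours UL by 0.10 × 500 − 10 = $40 with equal counts, and by 40 + 35 × 0.26 = $49 with fewer UL reinsertions.

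| Noise SD | Extra catheters, SL v UL | Wilcoxon declares UL dearer |
|---|---|---|
| $1 | 0.7 v 0.7 | 66% |
| $10 | 0.7 v 0.7 | 13% |
| $20 | 0.7 v 0.7 | 6% |
| $1 | 0.7 v 0.44 | 25% |
| $10 | 0.7 v 0.44 | 1% |

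If the premium applies to every catheter, it averages 1.7 × 10 = $17. With equal counts and R of $500 to $1,000 the mean then favours UL by $33 to $83, and the range is 16–65% for noise SD $20 to $1. Over all these settings the figure is about 1% to 67%.

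**3. Same model, no premium**

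With equal counts, Wilcoxon finds UL cheaper in 18–21% of trials and a Welch test on means in 55–59%. With 0.7 v 0.44 the figures are 68–78% and 64–75%.

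**4. A second model, built on failure rates, 91 per arm**

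SL failure is 45%. With hazard ratio 0.63, UL failure is 1 − 0.55^0.63 = 31%. Each failure costs $35, 20% of failures need a $1,000 rescue, the premium is $10 and the noise is small. The true mean difference is 10 + (35 + 0.2 × 1,000) × (0.31 − 0.45) = −$22.9. Wilcoxon was significant in the direction opposite to the observed mean difference in 68% of trials.

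**The case against.** Several points on the other side have force.

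- The term nonparametric summaries is not defined, and a bootstrapped mean could be read into it. The planned data allow a mean difference to be computed. That stands, but the text names no mean, and the one test it names is on ranks.
- Rescues are not lost from view. Counts per group are tracked, and Appendix C records the type of replacement access. A reader might infer that the plan ignores rescues altogether; it does not. What goes missing is their price, once the comparison is made on ranks.
- A reader might infer that a reversal is likely, or that some particular error rate applies. The documents do not support that. They give no UL premium, rescue price or rescue rate, and the 1.7 catheters come from a cited study rather than this population. Personnel time is to be valued in money, which may spread costs and weaken the effect of a small premium. If UL also prevents reinsertions, as the trial hypothesises, the ranks move in its favour.
- A reader might infer that the rank test is always the weaker one. It is not: with no premium, 0.7 v 0.44 extra catheters, noise SD $10, R = $500 and rescue in 10% v 6.3%, Wilcoxon found UL cheaper in 53% of trials and Welch in 26%.
- Cost is among the objectives that Study Design calls exploratory, and the sample size is not based on it. The sentence about millions of dollars is rationale, not an estimand.

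These points limit the size and the grade of the concern. They do not remove the mismatch between the objective and the method.

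**Conclusion.** The concern holds in a limited form. The objective depends on the arithmetic mean cost per patient, and the stated analysis does not estimate it. This follows from the documents alone and needs no outside figure. That the rank test can contradict the mean is shown by the fixed example. How often it would do so here cannot be settled from the documents: about 1% to 67% under a $10 premium with rescue in 15% v 5% at $500 to $1,000, and no general disadvantage in power if there is no premium and UL needs fewer reinsertions.

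The change should be made, since a method that answers the stated question is available from data already planned. It bears on an exploratory secondary/tertiary objective only; the primary survival comparison is untouched.

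**What to change.** State in Statistical Analysis that the main cost result is the difference in arithmetic mean cost per randomised patient, UL minus SL, with a bootstrap (or Welch) 95% confidence interval. Keep medians with interquartile ranges, the proportion needing PICC or CVC rescue, and the Wilcoxon test as supportive description, not as the basis of the cost conclusion. If a bootstrapped mean was already intended, one sentence saying so settles the point.

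For the same reason, reconsider valuing reinsertion time from the median, because a median multiplied by a count does not give a total.

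The cost is a short wording change and a few lines of SAS, with no new data. The downside is a wide interval, because rescue costs are skewed. In the fixed example at R = $500 the standard deviations are $148.0 (SL) and $102.5 (UL). The standard error is √((148.0² + 102.5²)/91) = $18.9, and the 95% interval is −19.0 ± 1.975 × 18.9, or about −$56 to $18. That interval shows an uncertainty about cost that the rank p-value conceals.

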We propose a prospective, single-site, parallel, two-arm randomized investigation of catheter survival when two catheter lengths are evaluated. Specifically, experimental ultra long IV (6.35 cm/20G) will be compared with conventional standard long IV (4.78 cm/20G). The primary objective of this study is to demonstrate that there is better IV survival when the quantity of catheter residing in the vein is enhanced. Patients with functional catheters less than 24 hours duration and discharged will be excluded from the survival analysis. Exploratory secondary and tertiary objectives and adjusted multivariable analyses on the primary objective will also be conducted.

Preliminary Data:

[figure not shown]
We prospectively enrolled 86 patients in our study and performed IV assessment after IV placement and within 24 hours, 48 hours, and 72 hours from time of IV placement to assess for functionality. The graph below highlights percent of the catheter in the vein as it relates to IV failure.

The table below highlights key study findings of statistical significance.

Percent catheter in vein versus longevity	IV Functional N=57	IV Failed N=29	p-value
Percent catheter in vein	Survival	Failure	
<30%	0/6 (0%)	6/6 (100%)	<0.0002
30-64%	48/71(67.6%)	23/71(32.3%)	
≥65%	9/9 (100%)	0/9 (0%)	

In our pilot study, **100% of catheters failed** in which less than 30% of the catheter was placed within the vein and **no catheters failed** in those IVs in which at least 65% or 3.1 cm of the catheter was in the vein. It is therefore our goal to place at least 3.1 cm of the catheter in the vessel lumen. To accomplish this task, a calculation can be performed to determine the minimum total catheter length that should be utilized to cannulate a vein at a specific depth. The figure below illustrates this calculation, which is based on the Pythagorean theorem. Given that the depth of the vein is a known variable, it is possible to determine the appropriate total catheter length required prior to starting the procedure to ensure that at least 3.1 cm of the catheter can be placed inside the vein. Based on this hypothetical model, it is possible to achieve the target catheter in vein length for depths less than or equal to 1.20 cm using the 4.78 cm option. Any depth greater than 1.20 cm would require a longer catheter. A key assumption is that inserters approach the target vein with a 45 degrees angle of insertion.

Study Population and Eligibility:

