Subjects will consist of a convenience sample of emergency department patients that require US-guided IV access. Eligible patients must be greater than 18 years old, and be self-identified as a difficult stick. The patient must also recount a prior emergency room visit or hospitalization in which more than 2 attempts were required to obtain access, have a history of a rescue catheter as the result of an inability to obtain a peripheral IV, or have one of the following conditions: end-stage renal disease on hemodialysis, IV drug abuse, or sickle cell disease.

Patients are excluded if they do not meet inclusion criteria, have participated in the study prior, have already undergone an attempt at vascular access or if the enrollment process has the potential to delay their care. Study participation is voluntary and written informed consent will be obtained. See Appendix A for Eligibility Checklist.

Numerous emergency room staff members are proficient in placing ultrasound-guided IVs. This includes physicians, nurses, and technicians. Staff will be enlisted on a voluntary basis to perform insertions on a voluntary basis.

Study Procedure:

Initial Assessment

Post-consent, eligible patients will be randomly allocated to the experimental group (forearm) or the control group (upper arm) in a ratio of 1:1 via a computer-generated randomization schedule. Research staff at the Department of Biostatistics will perform concealed immediate assignment by following a block scheme. Sealed envelopes containing the randomized IV access arm will be revealed at the bedside.

After patient enrollment, the insertion nurse or physician is engaged to perform the procedure. Only providers that are credentialed in ultrasound-guided vascular access will place catheters in study subjects. Vessel depth and diameter are measured by research staff and images are saved and archived for review by the Emergency Ultrasound Director. Vessel depth is measured on the ultrasound unit from the point of contact to the middle of the vein. All catheters are 20 gauge in diameter. The research staff will direct the inserter to choose the basilic, cephalic or brachial vein at least 2 cm above the antecubital fossa. If the patient is randomized to the control group, the inserter will place the Standard Long 4.78 cm catheter. If the patient is randomized to the experimental group, the inserter will place the Ultra Long 6.35 cm IV.

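### The exploratory Cox models for insertion angle and in-vein length ignore clustering by inserter, so their p-values may be too small if inserters differ in both technique and catheter survival

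*Combined protocol and SAP*

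**What the plan says.** Two of the secondary/tertiary objectives concern how the catheter lies: "Determine catheter survival based on angle of insertion" and "Determine optimal cutoff length of catheter in vein for best survival profile". Study Design sets their status: "Exploratory secondary and tertiary objectives and adjusted multivariable analyses on the primary objective will also be conducted". The Statistical Analysis section gives the method for testing catheter variables: "Cox proportional hazard regression models for time-to-event outcomes", with logistic regression for binary outcomes and a 0.05 threshold. It does not define the catheter variables; I take them to include angle and in-vein length, since both are survival objectives. It names no frailty, random effect, robust variance, stratification or covariate for the inserter.

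On who inserts, Study Population and Eligibility says "This includes physicians, nurses, and technicians" and "Staff will be enlisted on a voluntary basis to perform insertions". Study Site adds "Nearly forty ancillary staff members are certified in this procedure". Neither section says how many people will take part or how many catheters each will place. Study Procedure lists inserter details among the data collected, and Appendix B has ID fields for a first and a second inserter. Prior participants are excluded, so the unit that can repeat is the inserter, not the patient.

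**The concern.** Angle is set by the operator and is not randomised. In-vein length follows partly from angle. Catheters placed by one person may therefore resemble each other on the exposure and, through skill, site choice or securement, on survival too. When both hold, a standard error that assumes independent catheters is too small. A difference among a few busy inserters could then be reported as a significant effect of angle or length. Balancing inserters across arms would not cure this, because the comparison is between angles or lengths and not between arms.

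There are two separate problems. One is the error bars. The other is confounding between operators: those who use a given angle may differ in other ways that affect survival. They need different remedies. What is at stake is how far the angle and length results can be trusted; the catheter comparison itself is not at stake.

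**Working it through.** **The plan's own figures.** The documents give no figure for the angle or length analyses. The nearest is the total of 182 for the primary test (80% power, hazard ratio 0.63, control median 30 h, 10% dropout).
- Events, Schoenfeld, two-sided: 4 × (1.96 + 0.8416)² / (ln 0.63)² = 31.40 / 0.2135 = 147.1, so 148.
- Events, Freedman: (1.63 / 0.37)² × 7.849 = 152.3, so 153.
- Dividing by 0.9 gives 165 or 170 if every evaluable catheter fails. A total of 182 needs an unstated follow-up of about 5.5-6.5 days. The figure is compatible with its inputs but cannot be confirmed, and nothing below depends on it except as a count.

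**Inputs.**
- From the documents: 182 catheters, or 182 × 0.9 = 164 after dropout; control median 30 h; about forty certified ancillary staff, with physicians in addition.
- Assumed: number of inserters, evenness of load, share of the covariate's variance between inserters (ICCx), share of the outcome's variance between inserters (ICCy) or inserter log-hazard SD, and, in some of the simulations, a mean stay of 96 h.

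**Approximate design effect.** DEFF = 1 + (m(1 + CV²) − 1) × ICCy × ICCx, where m is catheters per inserter and CV is the coefficient of variation of load. Actual alpha = 2(1 − Φ(1.96/√DEFF)). With ICCy 0.02-0.10 and ICCx 0.3-0.5:

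| Inserters | m | Load | DEFF | Actual alpha |
|---|---|---|---|---|
| 40 | 4.55 | equal | 1.02-1.18 | 0.052-0.071 |
| 40 | 4.55 | CV 1 | 1.05-1.41 | 0.056-0.098 |
| 20 | 9.1 | equal | 1.05-1.41 | 0.056-0.098 |
| 10 | 18.2 | equal | 1.10-1.86 | 0.062-0.151 |

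Example, 20 inserters, upper end: 1 + 8.1 × 0.10 × 0.5 = 1.405; 1.96/√1.405 = 1.65; alpha 0.098. If either ICC is zero, DEFF is 1 and alpha is 0.05.

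**Simulation of the ordinary Cox test.** 164 catheters, a covariate with no effect, log-normal inserter frailty with SD 0.3-0.5, ICCx 0.3-0.5, 3,000 runs per setting (Monte Carlo SE about 0.004):
- 40 inserters: 0.057-0.082 with equal load, 0.063-0.108 with uneven load.
- 20 inserters: 0.068-0.106 and 0.082-0.144.
- 10 inserters: 0.084-0.164 and 0.085-0.187.
- No inserter effect on survival: 0.042-0.056.
- Randomised arm in place of the covariate: 0.040-0.063, so no inflation of the primary comparison.

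Further simulations with 15-40 inserters gave 5-10% in a milder setting (ICCx 0.3, SD 0.3) and 9-23% in a stronger one (ICCx 0.6, SD 0.5).

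**What the remedies do (15-40 inserters).**
- Shared frailty, parametric model: the false-positive rate fell from about 6-10% to 4-7% (milder) and from 11-23% to 6-9% (stronger). Standard errors rose 1-2% when inserters had no effect and about 6-25% when they did.
- Stratifying by inserter: false-positive rate 3-6%, but standard errors rose 32-64% (milder) or 66-118% (stronger). Information kept is 1/1.64² = 37% to 1/1.32² = 57%, and 1/2.18² = 21% to 1/1.66² = 36%.
- Cluster-robust variance: only a partial correction, about 7-10%, because there are few clusters.

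**In-vein length is less operator-driven than angle.** Under the right-triangle model in Preliminary Data, in-vein length = catheter length − depth / sin(angle). At 1.20 cm and 45 degrees the standard catheter gives 4.78 − 1.20/0.7071 = 3.08 cm, which reproduces the plan's 3.1 cm target. At the same depth and angle the ultra long catheter adds 6.35 − 4.78 = 1.57 cm. That part is fixed by randomisation, and depth is a feature of the vein.

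**The case against.** The strongest reply is that the premise is inferred. The protocol describes a wide pool of proficient staff, physicians come on top of the ancillary group, and no count of participants is given. With forty evenly used inserters the simulated false-positive rate is only 5.7-8.2%, and the upper figures need clustering values that no section supports. The analyses are declared exploratory. The adjusted multivariable models have no listed covariates, so inserter details could still be entered. All of this stands. It makes the size conditional and the priority low. It does not remove the gap, because the plan does not say that the recorded ID will be used, and voluntary enlistment makes uneven load plausible.

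A reader might go further in four ways that the documents do not support:
- **That the primary log-rank test or the sample size is undermined.** Allocation is by patient, and the simulated arm test held its level.
- **That the angle and length tests are certainly too optimistic.** This requires inserters to differ on both technique and survival, which the documents do not show.
- **That vein depth and the overall and first-stick success comparisons need the same treatment.** Depth is measured by research staff and is not shown to be operator-driven. The success objectives compare randomised arms. No calculation supports extending the point to either.
- **That stratifying by inserter is a nearly free remedy.** It gives up roughly 40-80% of the information on the covariate.

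**Conclusion.** The concern holds in a conditional form. The plan's Cox models for angle and in-vein length assume independent catheters, and the plan gives the recorded inserter ID no role. If inserters differ in both technique and catheter survival, the ordinary p-values may be too small. Under the assumptions of 15-40 inserters, 30-60% of covariate variance between inserters and an inserter log-hazard SD of 0.3-0.5, the false-positive rate is roughly 6-20% against a nominal 5%. It lies at the low end with many evenly used inserters, and there is no inflation if inserters do not affect survival. None of these assumed values comes from the documents. The point is strongest for angle and weaker for in-vein length. It sits between an optional improvement and a minor recommendation.

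**What to change.** In the Statistical Analysis section, state that the Cox models for insertion angle and in-vein length include a shared frailty for the inserter who placed the catheter (the second inserter where a rescue was needed). Report the number of inserters and the distribution of catheters per inserter, so that readers can judge how much clustering was possible.

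Add an inserter-stratified Cox model as a sensitivity analysis only. The frailty model largely corrects the error bars, but it assumes that the inserter effect is unrelated to the exposure and so does not remove confounding between operators. The stratified model compares catheters within inserter and addresses that.

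The cost is a few sentences of text and one model term; Appendix B already captures the ID. Intervals from the frailty model widen by about 1-2% if inserters have no effect and about 6-25% if they do. The stratified analysis is much less precise, with standard errors up about 30-120%, so a non-significant result there should not be read as evidence of no effect.
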